### 7.3 Subject Population(s) for Analysis

Any subject who receives at least one dose of treatment will be included in the safety analyses. For immunogenicity and survival/anti-tumor analyses, the main analyses will utilize subjects who received their assigned number of doses.

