**Post-Surgery:**

- 1) Subjects will be seen approximately 2 weeks ( $\pm 7$  days) post-surgery for follow up.
- 2) Subjects will undergo visual inspection to document healing by surgeon approximately 4 weeks post-surgery.
- 3) Post-surgery immunotherapy will proceed only after approval of the surgeon.
- 4) Subjects will receive up to 3 doses given 3 weeks ( $\pm 3$  days) apart. A total of 4 doses (pre- and post-surgery) will be administered.
- 5) Immunotherapy will be administered prior to adjuvant chemotherapy and/or radiation that may be indicated.
- 6) Adjuvant therapy will not be delayed for immunotherapy.
- 7) Subjects will be followed for tumor status as per institutional standard of care.

**COHORT II:** Immunotherapy will start approximately 2-6 months after completion of definitive or adjuvant chemoradiation therapy in order to allow recovery from the treatment side effects of chemoradiation. INO-3112 (6 mg of VGX-3100 and 1 mg INO-9012) will be delivered by IM injection with EP once every 3 weeks ( $\pm 3$  days) for a total of 4 doses. A minimum of 10 subjects will be enrolled into this cohort.

- 1) Subjects will be enrolled if they have HPV-16 and/or HPV-18 positive HNSCCa confirmed by ISH or PCR, and have completed chemoradiation therapy. Adequate tissue must be available to perform immunological correlates studies. Confirmation of HPV-16 and/or HPV-18 positivity is required prior to first dose of immunotherapy.
- 2) Subjects will be followed for tumor status as per normal institutional standard of care.

**Sample Size:** A minimal of 20 but no more than 25 eligible subjects will be enrolled in this study.

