  - ii. The Lytic Granule Loading assay will employ a 120-hour *in vitro* stimulation of unfractionated patient PBMCs using peptides spanning VGX-3100 antigens, an irrelevant peptide control (OVA) and a positive control (Concanavalin A). The Lytic Granule Loading assay will examine the following external cellular markers: CD3, CD4, CD8 (T cell identification), and CD137 (also known as 41BB – marker of T cell activation). The Lytic Granule Loading assay will additionally analyze the following intracellular markers: Granzyme A, Granzyme B, Granulysin and Perforin (proteins involved in lytic degranulation and cytotoxic potential). This panel of markers may vary as new information becomes available.
  - iii. The Killing assay will employ a 120-hour *in vitro* stimulation of unfractionated patient PBMCs using peptides spanning VGX-3100 antigens. Stimulated whole PBMCs or CD8+ T cells isolated after the 120-hour incubation will be co-incubated for 60 minutes with target cells that have received a membrane stain that differentiates them from patient PBMCs/CD8+ T cells and have additionally been pulsed with a reagent which is activated only when the cell is actively in apoptosis (programmed cell death). At the end of this time cells will be washed and target cells identified using the membrane stain and analyzed for the presence of the active substrate as a measure of functional cytolytic degranulation and killing. Employment of this assay may change pending readouts from the Lytic Granule Loading assay. Description of previous use of these assays or variants thereof can be found in Bagarazzi *et al.* Immunotherapy against HPV16/18 [12]. The construction of this assay may vary as new information becomes available.
4. Evaluate tumor infiltrating lymphocytes (TIL) by Immunohistochemistry (IHC) on pre-surgical and surgical samples. HPV immunotherapy prior to surgery will provide us with a unique opportunity to determine if the VGX-3100 induced immune response can directly target the HPV positive tumor cells. Therefore, we will perform immunohistochemistry on

samples obtained prior to or at study entry as well as on samples that will be obtained from resection of the primary tumor in Cohort I.

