## **4.4 Early Withdrawal of Subjects**

### **4.4.1 When and How to Withdraw Subjects**

Subjects who do not complete the study protocol will be considered to have prematurely discontinued the study. The reasons for premature discontinuation (for example, voluntary withdrawal, toxicity, death) must be recorded on the case report form (CRF). Final study evaluations will be completed at the time of discontinuation if it is possible. Reasons for withdrawal include, but are not limited to the following:

1. Inter-current illness that would, in the judgment of the investigator, affect assessments of clinical status to a significant degree or require discontinuation of study;
2. Unacceptable toxicity: Subjects will be followed until resolution or stabilization;
3. Disease progression;
4. Subject withdraws consent;
5. Treatment delay greater than four weeks for any toxicity;
6. Subjects who do not have satisfactory compliance with study procedures;
7. Major protocol violations, including, but not limited to:
  - a. failure to meet major inclusion/exclusion criteria;
  - b. failure to complete full evaluations as required by protocol;
  - c. use of concomitant therapies.

If any subject in a cohort discontinues early for reasons other than toxicity from immunotherapy, consideration will be given for replacement.

If a subject discontinues Study Treatments before completion of long term follow up for 6 months post the last dose of immunotherapy, all assessments for the end of Study Treatment visit and/or end of study visit should be performed.

Subjects who have disease progression confirmed and/or start new anti-cancer therapy will be discontinued from the study. In both Cohorts, subjects who progress in their disease, once confirmed, will be required to come for the end of the study visit. All subjects will be followed for survival status regardless of the cause of death.

In the case of a fatal outcome, all relevant information (including cause of death, autopsy report, ER/hospital record, concomitant medication, and relationship to Study Treatment or underlying disease) will be collected.

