### **4.4.2 Data Collection and Follow-up for Withdrawn Subjects**

Subjects taken off study due to treatment related toxicity will be followed until resolution or stabilization. All subjects will be followed for survival status regardless of the cause of death.

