## 7 Statistical Plan

### 7.1 Sample Size Determination

A minimal of 20 but no more than 25 eligible subjects will be enrolled, as described above. This study is an estimation study, and as such, a power calculation is not applicable. Regarding the primary analysis, 20 subjects will provide 95% confidence that the true incidence of SAEs is <17% if 0 SAEs are observed. If more than one subject in a cohort discontinues early for reasons other than toxicity from the immunotherapy, consideration will be given for replacement.

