### 7.2 Statistical Methods

The primary analysis will estimate safety parameters. The incidence of SAEs and the incidence of injection site reactions will be estimated along with exact Clopper Pearson 95% confidence intervals. Toxicity experience will also be recorded and summarized.

In secondary analyses, immune response parameters will be estimated. For continuous outcomes, the mean and 95% confidence interval will be calculated using a t-distribution approach, and for binary outcomes, the proportion and exact Clopper Pearson 95% confidence interval will be calculated.

In exploratory analyses, we will also estimate the distributions of progression-free survival (PFS) and overall survival (OS) will be estimated, and any observed anti-tumor responses will be summarized. PFS and OS will be measured from the time of instillation of the initial dose of immunotherapy. Both The variables will be potentially censored by the end of the subject's observation. These distributions will be summarized using Kaplan-Meier survival curves and estimated median time to event of each type. Anti-tumor response category frequencies will be calculated.

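### The main PFS, OS and anti-tumor analyses keep only fully dosed subjects while time runs from dose 1, so deaths and confirmed progressions before the last dose drop out; the same rule can discard Cohort I TIL pairs complete at surgery

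*Combined protocol and SAP*

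**What the plan says.** - **Analysis set (Section 7.3).** "For immunogenicity and survival/anti-tumor analyses, the main analyses will utilize subjects who received their assigned number of doses". Safety, by contrast, uses every subject with at least one dose.
- **Time origin (Section 7.2).** "PFS and OS will be measured from the time of instillation of the initial dose of immunotherapy". Subjects are censored at the end of their observation, and results are Kaplan-Meier curves and medians. No landmark, delayed-entry, all-treated or sensitivity analysis is described.
- **Discontinuation (Section 4.4.1).** "Subjects who have disease progression confirmed and/or start new anti-cancer therapy will be discontinued from the study".
- **Survival follow-up (Section 4.4.2).** "All subjects will be followed for survival status regardless of the cause of death".
- **Replacement (Section 7.1).** "If more than one subject in a cohort discontinues early for reasons other than toxicity from the immunotherapy, consideration will be given for replacement".
- **TIL (Section 3.2.2, item 4).** "Evaluate tumor infiltrating lymphocytes (TIL) by Immunohistochemistry (IHC) on pre-surgical and surgical samples". This is one of the secondary immune-response endpoints. In Cohort I it compares a sample from or before study entry with the resected tumor.
- **Cohort I dosing after surgery (Section 3.1).** "Post-surgery immunotherapy will proceed only after approval of the surgeon"; and "Adjuvant therapy will not be delayed for immunotherapy".
- **Cohort I dose count.** The synopsis and Section 3.1 give a total of 4. Table S1 gives 4 as a ceiling. Section 6.1.2 allows at most 2 doses before surgery and 1-3 after.

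**The concern.** Selecting subjects on completed dosing while counting time from dose 1 gives each analysed subject a stretch in which death was impossible, and in which a confirmed progression would have removed the subject. Such subjects are neither events nor censored observations; they are absent. Exclusions caused by death or progression push PFS and OS upward. Exclusions for other reasons (withdrawn consent, toxicity, no surgical approval, adjuvant therapy) could act either way. Anti-tumor response frequencies have the same weakness, because a subject who progressed early is not counted as a non-responder.

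There is no control arm against which the missing early events would show. Replacement restores the number of completers, not the excluded events.

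For TIL the problem is a needless loss. Both samples exist by the day of surgery, so a dose missed afterwards cannot have affected the pair, yet it can disqualify the subject. Cohort I may have only 5 subjects.

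**Working it through.** **The plan's own figure.** Section 7.1 says that 0 SAEs in 20 subjects puts the true incidence below 17%. The two-sided Clopper-Pearson limit is 1 - 0.025^(1/20) = 16.8%, so this reproduces. It concerns safety and does not depend on the completer rule. The plan gives no figure for PFS, OS or TIL.

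**Step 1: length of the window before the last dose (L).**
- Cohort II (4 doses, 3 weeks ± 3 days apart): 3 × 21 = 63 days; 3 × 18 = 54 to 3 × 24 = 72 with windows.
- Cohort I: no day is fixed. Assume surgery 14-28 days after dose 1 (and after dose 2 if two are given before surgery), and the first post-surgery dose at the 4-week inspection.
  - 1 + 3 doses: (14 to 28) + 28 + 42 = 84-98 days; with windows, 14 + 21 + 36 = 71 to 28 + 35 + 48 = 111.
  - 2 + 2 doses: (21 to 28) + 28 + 21 = 70-77 days; with windows, 18 + 21 + 18 = 57 to 28 + 35 + 24 = 87.

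Follow-up is 6 months (183 days) after the last dose, so T = L + 183. In Cohort II the window is 63/246 = 26% of planned follow-up (54/237 = 23% to 72/255 = 28%).

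**Step 2: illustrative size for PFS.** Let S be the true PFS at T in all dosed subjects. Assume a constant hazard, that every event before L removes the subject, and that nobody is removed for another reason. Then:
- PFS at T among completers = S(T)/S(L) = S^(183/T)
- expected excluded events per 20 dosed = 20 × (1 - S^(L/T))

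| True PFS at T | L = 54 | L = 63 | L = 111 | Excluded per 20 (L = 54 to 111) |
|---|---|---|---|---|
| 90% | 92.2% | 92.5% | 93.7% | 0.5-0.8 |
| 80% | 84.2% | 84.7% | 87.0% | 1.0-1.6 |

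Example: S = 0.90 and L = 63 gives 0.90^(183/246) = 0.925.

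For scale, the exact 95% interval is 68-99% for 18/20 and 56-94% for 16/20. PFS stays above 50% throughout, so the median is not reached in either population; the distortion would show in the curve and in any time-point rate. OS has the same direction for excluded deaths and is not sized here.

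**Step 3: TIL precision.** Treating TIL change as continuous, Section 7.2's t-based 95% half-width is t(0.975, n-1)/√n in SD units: 1.24 for n = 5, 1.59 for n = 4, 0.72 for n = 10 and 0.77 for n = 9. This applies only if the lost subject is not replaced.

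**The case against.** **Low stakes.** PFS, OS and anti-tumor response are exploratory, the study is an estimation study without a power calculation, and primary safety uses all dosed subjects. Calling these the main analyses leaves room for supportive ones. All of this stands and limits the weight of the point, but the plan specifies no supportive analysis that would correct the rule.

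**How many progressions are lost.** A reader might infer that most progressions before the last dose disappear. The documents do not show this. Table S1 lists tumor evaluation only at screening, Table S2 has no such row, and tumor status follows institutional standard of care. A progression confirmed only after the last dose stays in. Exclusion by definition applies to deaths; for progression it applies only to those confirmed in time to stop dosing, and their number is unknown.

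**Event rates.** Section 1.1.1 says at least 10-30% of such patients eventually recur. A PFS of 80% within about 8 to 10 months would already use two thirds of the top of that range, so the 90% row is the more moderate one. A reader might also suppose that events cluster early and the bias is much larger; nothing in the documents supports a particular share before the last dose.

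**TIL.** It is tempting to say that a subject with no post-surgery dose is certain to lose the TIL pair. That follows if 4 doses in total, or at least one after surgery, are required. If Table S1's ceiling defines the assignment, it need not follow. With the term undefined, the rule can drop the pair, and no more can be said. Replacement within the cap of 25 could also restore precision.

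**Conclusion.** The concern holds in limited form. As written, Sections 7.2 and 7.3 together exclude every death before the last dose and every progression confirmed before it, and these exclusions bias PFS and OS upward. Exclusions for other reasons have no predictable direction.

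The Cohort II window, about a quarter of planned follow-up, comes directly from the schedule. The Cohort I window is nominally longer (70-98 days), but only under the assumed surgery and resumption dates; time to surgery varies, so day 111 is not a firm upper limit.

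The illustrated shift is about 2-4 points at a true PFS of 90% and 4-7 points at 80%. It rests on a constant hazard and on every early event causing exclusion. Later detection of progression would reduce it; a front-loaded hazard would increase it. It is small beside the sampling error with 20 subjects, but it is systematic and easy to avoid.

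For TIL, a complete pair can be lost because of later doses that cannot have affected it. Whether that happens depends on what the assigned number of doses means in Cohort I, which the documents do not settle. Primary safety conclusions are not affected.

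**What to change.** 1. **PFS, OS and anti-tumor response (Section 7.3).** Make the main set all subjects with at least one dose, the set already defined for safety, with PFS and OS timed from dose 1. Report any completer analysis as a sensitivity analysis with a landmark at the last dose.
2. **TIL (Section 7.3).** Analyse all Cohort I subjects with at least one pre-surgery dose and evaluable paired tissue.
3. **Blood immunology.** The full-dose set may remain the main set.
4. **Cohort I dose count.** Reconcile the synopsis, Table S1, Section 3.1 and Section 6.1.2 so that the assigned number has one meaning. Which count applies is for the sponsor and investigators to settle.

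**Cost.** Two or three sentences in Section 7.3 and the reconciliation. No new data are needed, since survival status is already followed for everyone.

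**Downside.** Subjects who leave early without a recorded progression enter PFS and are censored when observation ends, possibly informatively. Report their number and reasons.

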**Table S1: Cohort I Schedule of Events**

Pre-surgery (Up to 2 doses of immunotherapy 3 weeks apart ± 3 days)

Post-surgery (Up to 3 doses of immunotherapy, 3 weeks apart; ± 3 days).

Subjects will receive no more than 4 doses of Immunotherapy (to include both pre and post-surgery dosing).

|  | Screening  | Pre Dose       | Post Dose      | Surgery | 2 wk Post surgery | Inspection Visit  | 2 wk f/u post last dose | LTFU/ EOS  |
|--|------------------------|----------------|----------------|---------|-------------------|-------------------------------|-------------------------|------------------------|
| Procedures  |                        |                |                |         |                   |                               |                         |                        |
| Informed Consent   | X                      |                |                |         |                   |                               |                         |                        |
| Medical History  | X                      |                |                |         |                   |                               |                         |                        |
| Physical Exam  /Assessment                         | X                      | X              |                |         | X                 | X                             | X                       | X                      |
| Performance Status (ECOG)                                      | X                      | X              |                |         | X                 | X                             | X                       | X                      |
| Concomitant Medications  | X                      | X              |                |         | X                 | X                             | X                       | X                      |
| Adverse Events   | X                      | X              | X              |         | X                 | X                             | X                       | X                      |
| Injection site assessment                                      |                        |                | X  |         |                   |                               | X                       |                        |

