| Research Immunology                                     |                        |                |                |         |                   |                               |                         |                        |
| Serum and Whole Blood (1 Red Top and 4 ACD tube)  | X                      | X              |                | X       | X                 | X                             | X                       | X                      |
| Tissue Sample                                     | X                      |                |                | X       |                   |                               |                         |                        |
| HLA Testing (no action required)                        |                        |                |                |         |                   | X                |                         |                        |
| IMMUNOTHERAPY   |                        |                |                |         |                   |                               |                         |                        |
| Download EP Data   |                        |                | X              |         |                   |                               |                         |                        |
| Patient Reminder Card  |                        |                | X              |         |                   |                               |                         |                        |

1- Screening to be done within 28 days prior to first dose. If a subject is rescreened, the screening clinical labs and 12-lead ECG must be repeated unless they will occur within 4 weeks of the subject's first dose. All other screening procedures do not need to be repeated.

2- Inspection visit occurs 4 weeks post-surgery (± 7 days)

3- LTFU: Long term follow up: every 3 months (±7 days) for 6 months from the last dose of immunotherapy, End of Study (EOS) defined as last LTFU visit

4- Includes weight, vital signs, oxygen saturation (height will be collected as part of Screening visit). Assessment includes

medical/clinical assessment

- 5- To be done 30-45 minutes post dose
- 6- If clinical screening labs (CBC and Chemistry) were performed within 72 hours prior the subject's first dose, these labs are not required to be redrawn prior to the subject's first dose

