### 3.1 General Design

**Study Schema:** Eligible subjects will receive highly engineered plasmid DNA encoding HPV-16 and HPV-18-E6 & E7 transcription unit antigens (VGX-3100) combined with the DNA encoding IL-12 (INO-9012) followed by EP with the CELLECTRA®5P device.

**COHORT I:** Immunotherapy will be given both before and after definitive surgery. Each subject will receive a total of 4 doses of treatment, 1-2 of them pre-surgery. Each treatment will be 6 mg

of VGX-3100 and 1 mg INO-9012 (INO-3112) delivered IM followed by EP. A minimum of 5 eligible subjects will be enrolled to this cohort.

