### **6.1.2 Visit for Immunotherapy (Pre and Post surgery: Every 3 weeks $\pm$ 3 days)**

Subjects may receive up to 2 doses of immunotherapy prior to surgery and 1-3 doses post-surgery as previously described. All sequential doses will be administered three weeks ( $\pm$ 3 days) apart.

The following study evaluations will be performed **prior to immunotherapy**:

1. Confirmation of p16 positivity or other pathological evidence of oncogenic HPV infection.
2. Medical/Clinical assessment including concomitant medications/treatments.
3. Focused physical examination including, but not limited to vital signs, weight and oxygen saturation.
4. ECOG Performance Status.
5. Review of adverse events.
6. Clinical laboratory testing including, but not limited to: CBC with differential and platelet count, total serum bilirubin, alkaline phosphatase, AST (SGOT), ALT (SGPT), serum creatinine, serum electrolytes, serum calcium and serum albumin.

NOTE: If clinical screening labs (CBC and Chemistry) were performed within 72 hours prior to the subject's first immunotherapy, these labs are not required to be redrawn prior to the subject's first immunotherapy.

7. Urine  $\beta$ -HCG (for women of child bearing potential) up to 72 hours prior to visit.
8. Whole blood and serum for baseline immunologic assays.

The following study evaluations will be performed on the same day **post-immunotherapy**:

1. Injection site reaction assessment within 30-45 minutes after EP.
2. Review of adverse events.
3. Data should be downloaded from the EP device.
4. Distribute participant reminder card to be reviewed at the next visit.

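### Section 7.3 may select the main Cohort I TIL analyses on post-surgery dosing, although the scheduled tumor tissue is complete at surgery

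*Combined protocol and SAP*

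**What the plan says.** **Analysis set.** Section 7.3 puts anyone with at least one dose into the safety analyses. For the rest it says: "For immunogenicity and survival/anti-tumor analyses, the main analyses will utilize subjects who received their assigned number of doses". The assigned number is not defined, and tissue endpoints are not mentioned.

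**Number of doses in Cohort I.** Section 3.1 says: "Each subject will receive a total of 4 doses of treatment, 1-2 of them pre-surgery". The synopsis also gives a total of 4. Table S1 treats 4 as a ceiling. Section 6.1.2 is looser: "Subjects may receive up to 2 doses of immunotherapy prior to surgery and 1-3 doses post-surgery as previously described".

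**Conditions on post-surgery dosing.** Under Post-Surgery, section 3.1 sets three conditions: "Post-surgery immunotherapy will proceed only after approval of the surgeon"; "Immunotherapy will be administered prior to adjuvant chemotherapy and/or radiation that may be indicated"; and "Adjuvant therapy will not be delayed for immunotherapy". Doses are 3 weeks apart, and the healing inspection is 4 weeks after surgery, give or take 7 days (Table S1).

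**Tissue.** Section 3.2.2 lists TIL by immunohistochemistry (item 4) and cultured TILs (item 5) among the correlative measures of immune response. Table S1 and section 6.1.3 schedule tissue only at screening and at surgery. Any later tissue is optional standard-of-care leftover (section 6.4).

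**The concern.** A full-dose analysis set normally ensures that everyone analyzed had the intended exposure before the outcome was measured. For TIL in the resected tumor, the relevant exposure is the one or two pre-surgery doses. The post-surgery doses come after the tissue has been taken. If they decide who enters the main analysis, the set is chosen by events after the measurement.

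Those events may not be neutral. Adjuvant therapy is given where indicated, which presumably depends on the disease found at surgery (an inference; the documents do not say so). Subjects lost to early adjuvant therapy may therefore have different tumors from those kept.

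At stake is the main TIL result in what may be a very small cohort. Pre- and post-immunotherapy tissue analysis is the first item under the Cohort I secondary objective (section 2.2), and section 3.2.2 presents pre-surgery dosing as a particular opportunity to see whether the immune response reaches the tumor.

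**Working it through.** **1. The plan's own figure.** Section 7.1 says that 0 SAEs in 20 subjects bounds the incidence below 17%. The two-sided Clopper-Pearson upper limit is 1 − 0.025^(1/20) = 16.84%, which agrees. It uses the safety set (at least one dose), so this point does not touch it.

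**2. Which number is assigned?** Section 3.1 lets the pre-surgery count vary (1 or 2) but fixes the total at 4, so 4 is the likelier reading. Section 6.1.2 leaves room for less. With at most 2 pre-surgery doses, a total of 4 needs 2 or 3 post-surgery doses. A single post-surgery dose therefore gives 1 + 1 = 2 or 2 + 1 = 3 in total.

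**3. Does 7.3 cover TIL?** Section 3.2.2 places TIL under immune response, so probably yes. Section 6.5 uses the word immunogenicity for blood samples, so this is a second condition.

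**4. Can a compliant subject stop short of 4?** Yes. Without the surgeon's approval there are no post-surgery doses. The other route is timing. The documents fix neither the first post-surgery dose date nor the adjuvant start. Assume the first post-surgery dose is at week 3, 4 or 5 (the inspection window), with exact 3-week spacing:

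- 2 pre-surgery doses: one further interval, so dose 4 falls at week 6, 7 or 8.
- 1 pre-surgery dose: two further intervals, so dose 4 falls at week 9, 10 or 11.

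An adjuvant start before that week leaves the subject below 4 with no deviation.

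**5. Do the withdrawal rules settle it?** No. Section 4.4.1 discontinues subjects who start new anti-cancer therapy. It does not say whether indicated adjuvant therapy counts, or whether a discontinued subject's TIL data stay in the main analysis. Sections 4.4.1 and 7.1 allow replacement to be considered; they do not require it.

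**6. Size of Cohort I.** The minimum is 5. The maximum is 25 in total less the Cohort II minimum of 10, which is 15.

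**7. Precision.** Section 7.2 uses a t-interval for continuous outcomes. In SD units the half-width is t(0.975, n−1)/√n:

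| n | Half-width (SD) |
|---|---|
| 3 | 4.303/√3 = 2.48 |
| 4 | 3.182/√4 = 1.59 |
| 5 | 2.776/√5 = 1.24 |
| 6 | 2.571/√6 = 1.05 |
| 7 | 2.447/√7 = 0.92 |
| 8 | 2.365/√8 = 0.84 |
| 10 | 2.262/√10 = 0.72 |

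The number dropped is an assumption throughout.

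- From 5 subjects without replacement: 1.24 becomes 1.59 if 1 is dropped and 2.48 if 2 are.
- From 5 with each dropped subject replaced: 7.3 stays at 1.24, against 1.05 (n = 6) or 0.92 (n = 7) if the replaced subjects' tissue were also used.
- From 10, dropping 2: 0.72 becomes 0.84.

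**8. Selection.** Let f be the fraction who stop early, and d the difference in mean TIL change between full-dose subjects and early stoppers, in SD. The overall mean is (1 − f) × full-dose mean + f × early-stopper mean, so the full-dose mean is off by f × d. With d assumed between 0 and 1, this is 0 to 0.20 SD at f = 0.2 and 0 to 0.40 SD at f = 0.4. Replacement restores the count but leaves this shift.

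**The case against.** The strongest reply is that the exclusion may never arise. It needs two readings at once. Section 7.3 says *their* assigned number, which could be set subject by subject. Section 6.5 uses immunogenicity for blood, sections 6.1.3 and 6.4 describe tissue work in other terms, and section 7.2 speaks more broadly of immune response parameters. If either reading fails, TIL is not restricted to four-dose subjects.

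Even if both hold, the documents give no rate of adjuvant therapy or early stopping. The worst precision figure needs minimum enrollment, 2 of 5 stopping early and no replacement. A shift of up to 0.40 SD is well inside the 1.24 SD half-width already accepted at n = 5. TIL is descriptive, with no test or stated decision rule. Section 7.3 governs only the main analyses, so a summary of all subjects with tissue is not barred. A single full-dose set also keeps blood and tissue results on the same subjects.

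Most of this stands as a limit on size and certainty. It does not remove the point. The total of 4 in section 3.1 and the listing of TIL under immune response in section 3.2.2 make the restrictive reading the likelier one. No all-tissue TIL analysis is specified. Keeping blood and tissue on the same subjects is no reason to let post-surgery doses select a result already fixed at surgery.

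A reader might infer that 7.3 definitely discards these subjects, or that it compromises the immune analyses as a whole. The documents support neither. The first depends on two undefined terms. For blood endpoints measured after the full course, a full-dose main set is defensible.

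**Conclusion.** The point holds conditionally. If the assigned number is 4 and immunogenicity includes TIL, following 7.3 as written selects the main Cohort I TIL estimate on events after the measurement and reduces its precision. Both conditions are likely; neither is certain.

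The loss depends strongly on cohort size: it can double the half-width at the enrollment minimum of 5 (2 dropped, none replaced) but adds only about 0.12 SD when 2 of 10 are dropped. A reader might take the doubling as the expected loss. The documents do not support that, because they give no early-stopping rate and Cohort I may have up to 15 subjects. The possible shift in the mean likewise rests on assumed values of f and d.

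The primary safety analysis, the 17% statement and the blood immune endpoints are not affected. Severity is minor to moderate: the endpoint is secondary and descriptive, but the rule does not suit it and is cheap to correct before results are seen.

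**What to change.** Amend section 7.3 as follows:

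1. For TIL by immunohistochemistry and for cultured surgical TILs, define the main analysis set as all Cohort I subjects with at least one pre-surgery dose and the tissue the endpoint needs (both entry and surgical tissue for immunohistochemistry). Inclusion should not depend on post-surgery doses, later discontinuation or replacement.
2. Show these TIL results by one versus two pre-surgery doses, since that is the exposure that precedes the tissue.
3. State that the assigned number of doses is 4 for the remaining immune endpoints, keeping the full-dose set as their main set.

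The range of post-surgery doses in section 6.1.2 can stay as it is. A supporting summary of blood endpoints in all dosed subjects would be optional and is not needed to correct this point.

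The cost is a few sentences in 7.3 and one analysis-set flag, with no added visits, samples or subjects.
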